The blind should be broken only if specific emergency treatment would be dictated by knowing the treatment status of the patient. If the blind needs to be broken, the Investigator should contact the Sponsor.

Amended to:

The blind should be broken only if specific emergency treatment would be dictated by knowing the treatment status of the patient. If the blind needs to be broken, the Investigator should

Verona Pharma plc CONFIDENTIAL Page 5 of 67

contact the Sponsor as soon as feasible. The investigator can unblind the investigational product immediately if he/she feels it is necessary without prior contact to the sponsor. However, the investigator should promptly document and explain to the sponsor any premature unblinding.

Section 5.8 Blinding, third paragraph Amended

from:

Note: Patients will also be aware of the appearance when pouring study medication into the nebulizer. Therefore, they should be instructed not to inform site personnel of the appearance of their study medication.

Amended to:

Note: Patients will also be aware of the appearance when pouring study medication into the nebulizer. Therefore, they should be instructed not to inform site personnel of the appearance of their study medication. Similarly, study personnel are not to discuss the appearance with patients. Patients will be instructed to seal the kit before returning it to the site at their next visit.

Section 6.4.3 Post-Dose Assessments Amended

from:

• Vital signs at 1, 2 and 3 hours

Amended to:

• Vital signs at 30 minutes and 1, 2 and 3 hours

Section 6.5.1 Pre-Dose Assessment:

The following bullets have been added:

• 12-lead ECG □ Vital signs

Section 6.5.3 Post-Dose Assessments Amended

from:

• Vital signs at 1, 2, 4, 6, 8 and 12 hours

Amended to:

• Vital signs at 30 minutes and 1, 2, 4, 6, 8 and 12 hours

Section 9.2.2.5 Efficacy

The following paragraph has been added:

Sites will be consolidated to the country level, which will be used as a fixed factor in all analyses in order to help reduce the variability in data. At least for the primary variable, secondary analyses investigating impact of country will be performed. Depending on differences in variance structure between countries, either separate models will be applied by country to estimate the treatment effect within each stratum or a full model including a

Verona Pharma plc CONFIDENTIAL Page 6 of 67

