- 20. A disclosed history or one known to the Investigator, of significant non-compliance in previous investigational studies or with prescribed medications.
- 21. Requirement for oxygen therapy, even on an occasional basis.
- 22. Any other reason that the Investigator considers makes the subject unsuitable to participate.
- 23. Known hypersensitivity to RPL554 or its excipients/components.
- 24. Abnormal clinically significant 12 lead Holter findings, including but not limited to:
 - Premature ventricular contraction (PVCs) >1000 in 24-hour period
 - Sustained ventricular tachycardia >6 beats
 - Atrial fibrillation with rapid ventricular response (>100 bpm)
 - Atrial flutter
 - Sinus pause >2 seconds

Verona Pharma plc CONFIDENTIAL Page 13 of 67

16 April 2017	
Study Medications:	All study medications will be administered using the inhaled route.
	Patients will be randomized to one of the following groups:
	RPL554 0.75 mg twice daily
	RPL554 1.5 mg twice daily
	RPL554 3.0 mg twice daily
	RPL554 6.0 mg twice daily
	Placebo twice daily
	Study medication will be blinded using a double blind technique.
	All study medication will be administered via a nebulizer.
	The study medication (RPL554 or placebo) will be administered using a standard jet nebulizer.
	The RPL554 formulation is a sterile suspension supplied as unit dose glass vials of sterile stock suspensions of micronized RPL554 in pH 7 phosphate buffered saline, containing surfactants to aid suspension. The placebo is the same as the RPL554 suspension except that the active RPL554 ingredient is omitted, i.e. it consists of pH 7 phosphate buffered saline and surfactants only.
Duration of Treatment:	The approximate planned duration for each patient will be up to 42 days: 2 to 14 days screening, followed by 28 days of treatment.
Criteria for Evaluation:	Treatments will be compared using (additive) analysis of covariance models adjusting for treatment, country/center and, if appropriate, baseline. Active treatments will first be compared to placebo using a closed test procedure (within substance) starting with the highest dose.

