9 STATISTICAL METHODS

9.1 Statistical and Analytical Plans

This section presents a summary of the planned statistical analyses. A detailed plan describing the analyses to be conducted will be defined before any analysis commences and will include the determination of rules for major and minor protocol deviations. Any deviation from the analysis specified in the protocol or the statistical analysis plan will be detailed and justified in the clinical study report.

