9.2.2.4 Extent of Exposure and Treatment Compliance

Compliance will be calculated based on two parameters – the number of used and unused vials returned and the dosing recorded in the e-diary. Total exposure will be based on the compliance with dose and the dose group the subject was randomized into. For in-clinic dosing, the RPL554 exposure will be calculated based on the nominal dose.

9.2.2.5 *Efficacy*

For FEV₁ the average effect (E_{av}) will be calculated as the AUC divided by the length of the time interval of interest. In addition, the peak effect on FEV₁ during these time intervals will be computed as the maximum value (E_{max}) and the trough FEV₁ as the value at 12 hours prior to next dose administration. Parameters will be calculated both over 3 hours (Visits 2 to 6) and over 12 hours (Visits 2 and 6). For withdrawn patients, values from last visit performed will be imputed. The peak FEV₁ is the highest value in the 3 hours after dosing.

Computed pharmacodynamic parameters for FEV_1 will be compared between the five study medications using (additive) analysis of covariance (ANCOVA) models with fixed factors for treatment and country(/center) and using the baseline FEV_1 (pre-dose at Visit 2) as a covariate. Parameters will be analyzed both after single-dose (Visit 2), at end-of-study (Visit 6/last visit) or as the average over Visits 3 to 6. The total score for the EXACT-PRO will be summarized for each day and the average weekly scores during the treatment period as well as the average over the full treatment period will be calculated. The average over last 7 days of the run-in period will be used as baseline.

Verona Pharma plc CONFIDENTIAL Page 55 of 67

Sites will be consolidated to the country level, which will be used as a fixed factor in all analyses in order to help reduce the variability in data. At least for the primary variable, secondary analyses investigating impact of country will be performed. Depending on differences in variance structure between countries, either separate models will be applied by country to estimate the treatment effect within each stratum or a full model including a treatment by country interaction term will be used to provide these estimates. No formal treatment by country test is planned.

The average daily use of rescue medication during the full treatment period and during each week will be calculated. The average over last 7 days of the run-in period will be used as baseline.

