Average EXACT-PRO total scores, average daily use of rescue medication, SGRQ-C total scores, MRC, global assessment of change, and TDI scores will be compared between the five treatments using ANCOVA models with treatment and country(/center) as factors and using baseline as a covariate where appropriate. Subdomain scores of the EXACT-PRO and SGRQC will be summarized and subjected to exploratory analyses.

The number of COPD exacerbations will be summarized by treatment group.

Testing for efficacy will start with the highest dose of RPL554 versus placebo. If a statistically significant difference is found, the testing will proceed with the next highest dose, and so on. Secondarily, the various doses of RPL554 will be compared. Appropriate measures will be taken to control for the type I error rate in these hypothesis tests. A closed testing procedure to test active dose vs. placebo will be used for the primary endpoint. The study is not powered for pairwise differences between active doses. Thus, dose-response is best investigated in a secondary analysis fitting an appropriate dose-response model to the data. The Statistical Analysis Plan will provide additional details of the multiplicity adjustment method(s) used.

All hypothesis testing will be done using two-sided alternative hypotheses. P-values less than 5% will be considered statistically significant.

9.2.2.6 *Safety*

Safety data, including safety laboratory tests, ECG parameters, Holter monitors, vital signs and physical examinations, will be summarized by treatment group and time point, when appropriate. For continuous variables, the change from baseline (both regarding pre-dose at Visit 2 and pre-dose at each treatment visit) to each post-dose time point will also be calculated and summarized. Data will further be illustrated by shift tables (showing changes from low/normal/high) and shift plots for selected time points.

Coded adverse event terms will be presented by system organ class (SOC) and preferred term and summarized by treatment group. A summary table by treatment group with total number and number of patients with adverse events, SAEs, adverse events leading to discontinuation of study medication, causally related adverse events and severe adverse events will be produced. Further SAEs, causally related adverse events and adverse event of each intensity will be summarized by SOC and preferred term.

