5.6.2. Analysis of Primary Endpoint

The primary efficacy analysis parameter is change from baseline FEV₁ to peak FEV₁ at Week 4 of treatment. The primary analysis will be based on the full analysis set.

Summary statistics for FEV₁ will be presented for baseline, week 4 and change from baseline by treatment group on patients with both assessments.

The primary analysis will use a restricted maximum likelihood (REML)–based repeated-measures approach. The change from baseline FEV₁ (at Day 1, Week 1, 2 3 and 4) will be the dependent variable. The analyses will include the fixed, categorical effects of treatment, visit, and treatment-by-visit interaction as well as the continuous, fixed covariates of baseline value. An unstructured (co)variance structure shared across treatment groups will be used to model the within-patient errors. If the model does not converge a compound symmetry (co)variance structure will be used. The Kenward-Roger approximation will be used to estimate denominator degrees of freedom and adjust standard errors. Analyses will be implemented with SAS PROC MIXED (see Appendix 4: SAS code for efficacy analysis). The primary comparison will be the contrast (difference in least squares mean [LSMEAN]) between treatments at Week 4.

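### The SAP's primary MMRM leaves out the country factor that the protocol puts in all analyses, plans no country analysis of the primary endpoint, and lists neither change

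*SAP*

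**What the plan says.** **Protocol.** Section 9.2.2.5 makes two commitments about country. "Sites will be consolidated to the country level", and country is then "used as a fixed factor in all analyses in order to help reduce the variability in data". Separately, "At least for the primary variable, secondary analyses investigating impact of country will be performed", through separate models by country or a model with a treatment-by-country term, and without a formal interaction test. The amendment summary records this paragraph as a deliberate addition. The synopsis describes "analysis of covariance models adjusting for treatment, country/center and, if appropriate, baseline", and 9.2.2.5 specifies "ANCOVA models with treatment and country(/center) as factors" for the symptom and rescue-use endpoints.

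**SAP.** The introduction says the plan is based on protocol version 2.0. The primary MMRM in 5.6.2 contains "fixed, categorical effects of treatment, visit, and treatment-by-visit interaction as well as the continuous, fixed covariates of baseline value". In Appendix 4, country is in the CLASS statement, but the MODEL statement has only treatment, visit, their interaction and baseline FEV1. Section 3.10 pools sites within countries for all analyses and defers the details to a step before database lock. Section 3.4 lists two changes from the protocol: LOCF ANCOVA to MMRM, and a new per-protocol set. The sensitivity analyses (5.6.2.1) and the seven subgroups (5.6.6) do not include country. Section 5.6.3 applies the primary model to the secondary and exploratory endpoints.

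**The concern.** A statistician following the SAP would fit a different primary model from the one in the protocol, and nothing in the SAP would alert a reader. That model gives the p-values for the fixed-sequence test of the four doses. Two planned elements are lost without a stated reason: an adjustment that the protocol adopted to reduce variability, and the country-level view of the treatment effect on the primary endpoint. The unused CLASS entry and the pooling rule that no model term uses suggest a drafting slip, but the documents do not settle that.

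Validity is not at stake. Protocol 5.7 describes equal randomization and mentions no stratification by country, so the test without country is valid. What is at stake is agreement between the two documents, possibly some precision, and the missing country estimates.

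**Working it through.** **1. The passages compared**

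| Item | Protocol 9.2.2.5 | SAP |
|---|---|---|
| Country in the primary model | Fixed factor in all analyses | Absent from the 5.6.2 text and the Appendix 4 MODEL; in CLASS only |
| Impact of country on the primary variable | Planned, estimates only | Absent from 5.6.2.1 and 5.6.6 |
| Change recorded | n/a | Not in 3.4 |

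A variable named in CLASS but not in MODEL (or in another effect) does not alter the fit. The SAP's text and code agree, so the model it specifies is unambiguous.

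**2. The plan's own sample size**

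Inputs (protocol 9.3, SAP 3.3): SD 250 mL, difference 111 mL, two-sided 5%, 80% power.

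n per group = 2 × (1.960 + 0.842)² × 250² / 111² = 79.6, rounded up to 80. Normal-approximation power at 80 per group is 80.2%. The stated figure reproduces and is not in dispute.

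**3. Reference case without country**

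Using the noncentral t, five arms of 80 and one baseline covariate:

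- df = 400 − 5 − 1 = 394
- SE = 250 × √(2/80) = 39.53 mL
- power at 111 mL = 79.99%; detectable difference at 80% power = 111.0 mL

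**4. Adding country**

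The documents give neither the number of countries (k) nor the share of residual variance that country explains (R²). Both are assumed here, and 250 mL is taken as the SD without country.

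- df = 394 − (k − 1)
- f = 1 + (k − 1)/(df − 1), the cost of chance imbalance when allocation is not balanced by country: 1.0026, 1.0103, 1.0234 for k = 2, 5, 10 (simulated over 1,500 unstratified allocations: 1.0026, 1.0101, 1.0232)
- SE = 250 × √(1 − R²) × √((2/80) × f)

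Power at 111 mL, with the detectable difference in brackets:

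| k | R² = 0 | 2% | 5% | 10% |
|---|---|---|---|---|
| 2 | 79.9% (111.2 mL) | 80.7% (110.0) | 81.9% (108.3) | 83.9% (105.5) |
| 5 | 79.6% (111.6 mL) | 80.4% (110.5) | 81.6% (108.8) | 83.6% (105.9) |
| 10 | 79.1% (112.3 mL) | 79.9% (111.2) | 81.1% (109.5) | 83.1% (106.5) |

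Against 79.99%, the net change runs from −0.9 points (k = 10, R² = 0) to +3.9 points (k = 2, R² = 10%). Country pays for itself once R² exceeds about 0.3%, 1.0% or 2.3% for k = 2, 5, 10.

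**5. If 250 mL is the SD within country**

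The planned model includes country, so this reading is also open. Leaving country out then raises the SD to 250/√(1 − R²) = 252.5, 256.5 and 263.5 mL at R² = 2, 5 and 10%. Power falls to 79.2, 77.9 and 75.7%.

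**6. Check in the repeated-measures model**

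Assumptions: complete data, five visits, SD 250 mL, k = 5, R² = 5%, country effect constant over visits.

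| Within-patient correlation (assumed) | No country | Country main effect | Country-by-visit |
|---|---|---|---|
| 0.5 | 39.55 mL | 38.63 mL | 38.69 mL |
| 0.8 | 39.57 mL | 38.71 mL | 38.74 mL |

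The entries are Week 4 SEs. The form in which country enters hardly matters.

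**7. Precision of country-level estimates**

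With equal-sized countries, the SE of one dose-placebo difference within a country is 250 × √(2/(80/k)) = 55.9, 88.4 and 125.0 mL for k = 2, 5, 10.

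**The case against.** The strongest reply is that SAP 3.4 announces a new primary method and 5.6.2 sets out all its terms, so the change is disclosed in substance. This does not hold. The only rationale in 3.4 is bias under LOCF, a missing-data argument that gives no reason to drop country; an MMRM can include it. The entry also cannot cover the separate country-impact analysis.

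The LOCF ANCOVA in 5.6.2.1 states no covariates, so it may still carry country from the protocol's model. That is possible, but a sensitivity analysis does not restore the primary model or give treatment estimates by country. Likewise, the later document promised in SAP 3.10 concerns how sites are pooled, not which terms enter the model.

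Three points stand:

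- The cost of adding country depends on allocation. If treatment were balanced within country, f would be 1 and power at R² = 0 would stay at 80.0%, so the 0.9-point cost and the break-even values would all but disappear.
- The country-level estimates would be imprecise, with SEs of about 56 to 125 mL against a target of 111 mL. They can only be descriptive, which fits the protocol's decision not to test.
- Timing matters. The SAP is dated 6 March 2018 and labelled for use after database lock. A change to the primary model is a simple correction only before unblinding.

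**Conclusion.** The concern holds. The SAP's primary model contradicts the protocol on which it says it is based, the planned country analysis of the primary endpoint is missing, and SAP 3.4 records neither departure. Section 5.6.3 carries the omission to the other endpoints, which the SAP treats as exploratory.

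The consequence is moderate. No bias, type I error inflation or error in the 80% power claim is shown. With 250 mL as the SD without country, adding country shifts power by −0.9 to +3.9 points. With 250 mL as the SD within country, omission lowers power from 80.0% to as little as 75.7%. Both ranges rest on an assumed R² of 0 to 10%; the first also assumes 2 to 10 countries and allocation not balanced by country. The point should be fixed because the SAP as written produces a different primary analysis from the protocol's, not because a precision loss is demonstrated.

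**What to change.** Before unblinding:

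1. Add country to the model text in SAP 5.6.2 and to Appendix 4, for example `model outcome = trt visit trt*visit country b_fev / ddfm=kr;`. A main effect matches the protocol's additive model; state that choice.
2. State the covariates of the LOCF ANCOVA in 5.6.2.1 and include country among them.
3. Restore the treatment estimates by country for the primary endpoint, by separate models or a treatment-by-country term as protocol 9.2.2.5 allows. Present them descriptively and without a test.

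If country was removed on purpose, list both departures in SAP 3.4 with reasons and delete country from CLASS. The study report must then cover them, since protocol 9.1 says: "Any deviation from the analysis specified in the protocol or the statistical analysis plan will be detailed and justified in the clinical study report".

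The cost is SAP wording, one changed MODEL line and the code for the country estimates, with no new data. The primary model spends one degree of freedom per additional country. It could lose up to about 0.9 power points if country explains nothing, there are 10 countries and allocation is not balanced by country.

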5.7 Method of Assigning Patients to Treatment Groups

All patients consented will be assigned a patient identification (PID) number upon signing of the informed consent using the following convention: XXX-YYY where XXX is the center number and YYY is the patient number (001, 002, etc.). Patients will receive one of the five different treatment options in the study (see Section 5.1). Patients will be equally randomized to one of the four doses or placebo before the first study medication administration at Visit 2. Medication identification numbers will be provided on the study medication kit.

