6.2 Visit 1: Screening

Written informed consent will be obtained by the Investigator as specified in Section 10.3 prior to any study related procedures being performed. This typically will need to be performed prior to the day of the screening visit to allow for discontinuation of any prohibited medications, including the requirement to refrain from bronchodilators in accordance with Section 5.9.1.

Patients will be screened to determine eligibility against the Inclusion and Exclusion Criteria between 7 and 14 days before the first dose of study medication at Visit 2. There are no fasting requirements for the screening visit. Patients must observe the medication restrictions described in Section 5.9.1, and other restrictions described in Section 6.1.

To account for diurnal variability in pulmonary function, Visit 1 is to take place in the morning. The following assessments will be performed, generally in the order indicated: □ Obtain informed consent (if not done prior to Visit 1)

- Demographic information
- Medical/surgical and disease history
- Prior medications and therapies
- Vital signs (blood pressure and pulse rate)
- Physical examination
- 12-lead ECG
- Pre-albuterol/salbutamol spirometry
- Reversibility test (four puffs of albuterol/salbutamol)
- Post-albuterol/salbutamol spirometry 30 minutes after albuterol/salbutamol dosing
- Blood and urine samples for laboratory safety tests and viral serology
- Serum pregnancy test (female patients of childbearing potential)
- Chest X-ray (unless historical X-ray performed in last 12 months is available)
- Questioning for adverse events (if informed consent obtained prior to Visit 1)

Patients meeting all of the Inclusion and none of the Exclusion Criteria will then have the following performed:

Verona Pharma plc CONFIDENTIAL Page 39 of 67

- Holter monitor placement (to be removed 1 day later)
- Dispensing of albuterol/salbutamol and, if applicable, inhaled steroids (see Section 5.9.1)
- Dispensing of e-diary and instructions on its use. The patient will log into the electronic Patient Reported Outcome (ePRO) device and answer all of the questions to ensure comprehension (see Section 7.2.2)

The patient will be instructed on the following:

- Return the next day for removal of Holter (noted as Visit 1B in Table 3)
- Return in 7 to 14 days for Visit 2

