7.2 Efficacy Assessments

7.2.1 Pulmonary Function Tests

Spirometry assessments (FEV₁ and FVC) will be made at the following time points at Visits 2 and 6 (\pm 10 minutes): pre-dose (one measurement at 15 minutes prior start of dosing) and 30 minutes and 1, 2, 3, 4, 6, 8 and 12 hours post-dose (after completion of nebulization) in accordance with ATS/ERS guidelines (Miller et al., 2005). At all time points, three technically acceptable measurements should be made and recorded. Spirometry assessments may be repeated up to eight times to obtain three acceptable readings according to ATS guidelines (Miller et al., 2005). The highest FEV₁ and FVC readings from each assessment will be used

Verona Pharma plc CONFIDENTIAL Page 44 of 67

for analysis even if the FEV_1 and FVC values come from two different forced exhalations. At Visits 3 to 5, spirometry will be made 15 minutes pre-dose and 30 minutes, and 1, 2 and 3 hours post-dose (\pm 10 minutes). Spirometry will be performed using equipment provided by the Sponsor and reviewed centrally, and sites will be instructed in proper use of the equipment prior to study initiation.

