3.3. Determination of Sample Size

The standard deviation for peak FEV1 is estimated to be 250 mL. With a 2-sided test at a 5% significance level and 80 evaluable patients per group, there will be an 80% power to detect a true difference of 111 mL between any two treatments. This detectable limit has been considered sufficient to conclusively identify a minimal effective dose of RPL554. Thus 80 patients per group will be randomized for a total of 400 patients.

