9.4. Appendix 4: SAS code for efficacy analysis

```
proc mixed data=efficacy;
class subject trt country visit;
model outcome= trt visit trt*visit b_fev /ddfm=kr;
repeated visit/ sub=subject type=un;
lsmeans trt*visit/ cl diff;
```

run;

where outcome is the change from baseline

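### Minor, free improvement: the primary MMRM uses one baseline-FEV1 slope for Day 1 to Week 4 and leaves out the Visit 1 pre-albuterol FEV1, giving up a little precision in the Week 4 contrast.

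*SAP*

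**What the plan says.** SAP 5.6.2 models change from baseline FEV1 at Day 1 and Weeks 1 to 4. It has treatment, visit and treatment-by-visit, "as well as the continuous, fixed covariates of baseline value", and an unstructured covariance with compound symmetry as fallback. The code in SAP Appendix 4 agrees: "model outcome= trt visit trt*visit b_fev /ddfm=kr". Neither contains a baseline-by-visit term.

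Baseline is the Visit 2 pre-dose assessment (SAP 5.1, 5.5.1). Protocol 7.2.1 describes it as "one measurement at 15 minutes prior start of dosing", recorded as the highest of three acceptable efforts.

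At Visit 1, Protocol 6.2 lists "Pre-albuterol/salbutamol spirometry". Protocol 6.3.1 uses that value once more, requiring the Visit 2 pre-dose FEV1 to lie within 20% of it. No model in the SAP uses it.

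Protocol 9.2.2.5 had planned ANCOVA with the Visit 2 baseline as covariate, fitted to the single-dose and end-of-study values separately, so Week 4 would have had its own slope. SAP 3.4 explains the move to MMRM by the handling of missing data and does not mention this side effect.

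**The concern.** A common slope is harmless if change from baseline relates to baseline in the same way at every visit. Here it probably does not. A patient who happens to be low on the morning of Visit 2 is low for both the baseline and the Day 1 peak, so that deviation cancels from the Day 1 change. It does not cancel from the Week 4 change, which therefore regresses more steeply on baseline. With an unstructured covariance, the fit draws the common slope towards Day 1, the least variable visit, and the Week 4 contrast gets less baseline correction than it should. Placebo is the comparator at all four steps of the fixed sequence (SAP 5.6.4), so a chance imbalance in that arm touches every step.

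The second part concerns efficiency. A second pre-randomization FEV1 carries information on each patient's underlying level. The sample size has no allowance for dropout (SAP 3.3) and discontinued patients are not replaced (Protocol 4.3.4), so precision available at no cost is worth taking.

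**Working it through.** **1. The plan's own figure.** SAP 3.3 assumes an SD of 250 mL for peak FEV1, two-sided testing at 5% and 80 evaluable patients in each arm, and concludes: "there will be an 80% power to detect a true difference of 111 mL between any two treatments". Allocation is equal across the five arms (Protocol 5.7).

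- SE of a contrast = 250 × √(2/80) = 39.5 mL.
- Detectable difference = 39.5 × (1.960 + 0.842) = 110.7 mL.
- Power at 111 mL = Φ(111/39.5 − 1.960) = 0.802.

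The figure reproduces. I take 250 mL as the SD left after baseline adjustment; the documents do not say which SD it is.

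**2. Why the slopes differ.** Write an FEV1 reading as true level (SD τ) + day effect (SD d) + measurement error (SD m), and add a patient-level response after dosing. The slopes of change on baseline are:

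- Day 1: −m²/(τ² + d² + m²)
- Week 4: −(d² + m²)/(τ² + d² + m²)

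None of these SDs is in the documents. With assumed middle values τ = 450, d = 130, m = 50 mL, the denominator is 202,500 + 16,900 + 2,500 = 221,900. Day 1 slope = −2,500/221,900 = −0.011. Week 4 slope = −19,400/221,900 = −0.087. The common slope fitted under unstructured covariance is about −0.02.

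Under the compound-symmetry fallback with complete data, the common slope would be the plain average over visits, (−0.011 − 4 × 0.087)/5 = −0.072. The amount of correction at Week 4 therefore depends on which covariance structure converges. With visit-specific slopes and complete data it does not.

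**3. Effect of the common slope, before the 20% rule.** Baseline SD = √221,900 = 471 mL, so a 1-SE imbalance between two arms is 471 × √(2/80) = 74 mL.

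- Shift in the Week 4 contrast = (0.087 − 0.02) × 74 ≈ 5 mL.
- Added variance = (0.067 × 471)² ≈ 996, against 250² = 62,500: about 1.6%.

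**4. Bias and error rate.** A simulation of 4,000 trials (5 × 80 patients, no effect, complete data; τ = 500, d = 150, m = 50 mL, no 20% rule) gave:

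| | Common slope | Visit-specific slopes |
|---|---|---|
| Mean estimate (true value 0), mL | 0.4 | 0.5 |
| SD of estimate, mL | 40.2 | 39.6 |
| Type I error | 0.053 | 0.051 |
| Mean estimate when imbalance exceeded 1 SD (average 126 mL), mL | −10.8 | −1.4 |

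The shift is conditional on imbalance and averages out over randomizations.

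**5. Adding Visit 1 FEV1, before the 20% rule.** Residual variance includes the uncertainty about the true level. With v = d² + m² = 19,400:

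- One reading: 1/(1/202,500 + 1/19,400) ≈ 17,700.
- Two readings: 1/(1/202,500 + 2/19,400) ≈ 9,260.
- Saving ≈ 8,440/62,500 = 13.5%.

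**6. Applying the 20% rule.** The rule removes patients whose two readings disagree most, and that disagreement is the source of the gain. Assumed ranges: τ = 450, d = 100 to 160, m = 40 to 60, response SD 150 to 200 mL, mean FEV1 1.3 to 1.6 L. With the rule applied:

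- Shift per 1-SE imbalance: 2.5 to 5.4 mL.
- Variance cut from visit-specific slopes: 0.4 to 1.6%.
- Further cut from Visit 1 FEV1: 5.5 to 9.4%, equivalent to 80 × (1/0.945 − 1) ≈ 5 to 80 × (1/0.906 − 1) ≈ 8 patients per arm.

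**7. Power at 111 mL.** Combining the low ends, the variance ratio is 0.996 × 0.945 = 0.941, so SE = 38.3 mL and power is 82.5%. Combining the high ends, 0.984 × 0.906 = 0.892, so SE = 37.3 mL and power is 84.5%. The low and high ends do not fall in the same scenarios; taken scenario by scenario, power is about 83 to 84%.

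**The case against.** The strongest reply is that the missing interaction is trivial and the second covariate optional. A shift of 3 to 5 mL is small beside an SE near 40 mL and a design difference of 111 mL. Most of the gain comes from Visit 1 FEV1, and using only the Visit 2 baseline is what Protocol 9.2.2.5 specifies. That stands, and it is why this is a minor point and not an error in the plan.

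A reader might infer more than the documents support:

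- **That the primary contrast is biased or its error rate inflated.** Randomization keeps it unbiased on average, and simulated type I error stayed near 5%.
- **That the baseline reading is noisy.** No within-patient variability is given anywhere, and the reading is the best of three acceptable, centrally reviewed efforts. Measurement error in a baseline covariate costs precision but does not bias a randomized contrast.
- **That power would reach 84 to 86% or more.** That follows only if the 20% rule is ignored.
- **That Visits 1 and 2 are under the same bronchodilator conditions.** Protocol 3.1 places washout of long-acting agents after screening, while Protocol 5.9.1 requires withholding before Visit 1. These passages need reconciling. If the visits are less comparable the gain shrinks, but a pre-randomization covariate with its own coefficient cannot bias the contrast.
- **That every secondary endpoint is affected.** SAP 5.6.3 drops baseline for PGAC and summarizes exacerbations by counts. The same-morning mechanism needs a Day 1 post-dose value, which trough FEV1, the symptom diary and the questionnaires do not have (SAP 5.2, 5.3).

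The LOCF ANCOVA in SAP 5.6.2.1, fitted at Week 4, would carry its own slope and is a partial check. It lists no covariates, however, and relies on the imputation that SAP 3.4 moved away from.

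**Conclusion.** The point holds as a minor, free improvement. The model shares one baseline slope across visits whose slopes plausibly differ, and it leaves a collected pre-randomization FEV1 unused. The cost is a conditional shift of about 3 to 5 mL per 1-SE baseline imbalance and roughly 6 to 11% of the variance of the Week 4 contrast, most of it from the unused reading. Power at 111 mL would be roughly 83 to 84% instead of 80%.

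These sizes rest on assumed variances and mean FEV1, on a response independent of FEV1 level, on 250 mL being the residual SD, and on complete data; dropout was not quantified. The direction does not depend on the exact values. Validity of the primary test is not in question.

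**What to change.** Before unblinding, in SAP 5.6.2 and Appendix 4, use for the FEV1 endpoints:

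`model outcome = trt visit trt*visit b_fev b_fev*visit scr_fev scr_fev*visit / ddfm=kr;`

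where `scr_fev` is the Visit 1 pre-albuterol FEV1. Keep the endpoint as change from the Visit 2 pre-dose reading. In SAP 5.6.2.1, name the covariates of the LOCF ANCOVA.

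The cost is SAP wording and nine parameters (four for `b_fev*visit`, five for `scr_fev` and its interaction) on about 400 patients. No new data are needed, and because of the 20% rule Visit 1 FEV1 should exist for every randomized patient. Baseline-by-visit for non-FEV1 endpoints is optional; it does not apply to PGAC or exacerbation counts.
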